10.4. Questionnaire Measures

Demographics:

Participants will be asked to complete a demographic questionnaire at baseline, which will assess relationship status, age, employment status, and ethnicity (See Demographic questionnaire).

Contraception questionnaire:

Participants will be asked to complete a questionnaire at baseline, and at 3 and 6 month follow-up to assess what contraceptive methods, if any, they are using currently or have used before (baseline) or since enrolling in the study (at follow-up). Participants who are currently using contraception will be asked how satisfied they are with the method. At follow-up only, participants will be asked if they have had a pregnancy and, if they have, the outcome of the pregnancy (ongoing, gave birth, miscarried, terminated, or prefer not to say). All participants are asked at baseline, 3 and 6 months, whether they have been told by a doctor or other health professional that they have a sexually transmitted infection.

Service use related to contraception and sexual health:

Participants will be asked to specify where they go to get their contraception and if they pay for it themselves.

Interaction with the intervention

In order to assess engagement with the intervention (and whether this is related to outcome), we will record website usage. The software used will record the number of times

each user visits the site, the amount of time spent on the site, the pages visited, and the amount of time spent on each page.

Methods to protect against sources of bias

Participants will provide baseline data on the tablet device before randomisation. Once eligibility for the study is established, and baseline data are collected, allocation to intervention or control group will be determined from the randomisation list, and this will not be changeable by participants or researchers. Subsequent outcome data will be collected online using an emailed weblink to the online outcome questionnaire. Data will be saved on an encrypted server, and data exported will be identifiable by study ID numbers only. Most data collection procedures are therefore automatically blind to allocation to intervention or control group, since they are automated. Sealed envelope will grant access to group allocation only to those who need to know, to for data analysis.

To maximise retention, we plan to make phone calls to non-responders (conducted by the trial co-ordinator), and it could be that group allocation is revealed by participants during the phone call. Data analysis for the primary outcomes will be conducted by statisticians who are blinded to group allocation.

[figure not shown]
Maximising retention

Our experience in the Sexunzipped and Men's Safer Sex online RCTs indicates that follow-up by email is acceptable to participants with email accounts. The Txt2Stop smoking reduction trial obtained their excellent follow-up using multiple methods of contacting people;²⁰ similar methods will be used for the present study:

- 1. Automated Email, with 3 further follow-up emails at weekly intervals
- 2. 2 text messages at the same time as the last two emails
- 3. One phone call a week after the final email
- 4. One final questionnaire by post

We will offer participants a £10 voucher for filling in the online questionnaire at 3 months, and a further £10 for the 6 month follow-up questionnaire. Incentives (a shopping voucher) will be sent by email.

Figure 2 Follow-up procedures

Lost to follow-up

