4. SUMMARY

Reducing unintended pregnancy is a national and global priority, and improving women's choice of contraception is a vital step. There are many myths, misunderstandings and concerns about contraception, and increasingly women turn to online resources for information on healthcare.

The aim of the study is to develop and test the feasibility of an online trial of a website to increase the acceptability, uptake and adherence to long-acting reversible contraceptive (LARC) methods in young women. LARC methods include the intrauterine device (IUD), intrauterine system (IUS), subdermal implant (SDI) and depo injection.

In Phase 1 of this study (completed) we developed a self-guided website that presents recommended contraceptive options in response to women's preferences. The website will be presented on a touch-screen tablet computer in clinic waiting areas or pharmacy consulting areas.

In Phase 2 (this study), we will assess feasibility of an online trial of the contraception choice website in five sites:

An NHS sexual health service (Margaret Pyke Centre, MPC)

A local general practice

A maternity service (Ashford & St Peter's Hospitals NHS Foundation Trust)

A community pharmacy (Greenlight)

An abortion service (bpas)

Phase Two will take 15 months including:

- Conducting a randomised pilot trial across the five settings
- Conducting a qualitative process evaluation of the website, of NHS implementation issues and of research procedures
- Analysis, reporting and dissemination of study findings
- Preparation of outputs, including a protocol for a definitive RCT to increase uptake and adherence of LARC that is informed by both quantitative and qualitative findings In each setting we will recruit 80 women aged 15-30 years (40 randomised to intervention and 40 to control) and follow them up by online questionnaire at 3 and 6 months (or 2 months after delivery for post-partum women).
- *Funder-approved amendment to recruitment*. In addition to the above, we will recruit 530 more women from one site only, the Margaret Pyke Centre, via their Central (telephone) Booking System. Women requesting an appointment for

contraception will be invited to go online and enter the trial before they attend their appointment.

Data collection:

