8. OUTCOMES

Funder-approved Amendment to outcomes measures: (this effectively converts the secondary outcomes related to contraception into primary outcomes)

Primary Outcomes

- LARC method in use at 6 months measured by response to study outcome questionnaire
- Satisfaction with any chosen method of contraception at 6 months measured by response to study outcome questionnaire using a Likert scale 1-5. *How satisfied are you with the contraception you are using currently?*

Secondary Quantitative Outcomes

- Follow-up rate at 6 months after randomisation
- Recruitment rate measured via the trial website as the time taken to recruit (up to 80) women in each site. Recruitment is assessed by completing (in full or in part) the baseline questionnaire.
- Effectiveness of contraceptive method in use at 6 months measured by response to study outcome questionnaire and grouped as follows from least to most effective: no method; withdrawal or natural method; condoms or diaphragm; pill, patch or ring; LARC or sterilisation
- Change in method between baseline and 6 months, indicating whether any change is to a method of greater, lesser or similar effectiveness (based on grouping above)
- Pregnancy by 6 months measured at 3 months and at 6 months by response to study outcome questionnaire
- Sexually transmitted infection diagnosis by 6 months measured at 3 months and 6 months by response to study outcome questionnaire.

Health service and out-of-pocket costs for contraception and other sexual health services - measured at 3 months and at 6 months by response to study outcome questionnaire

Secondary Outcomes – qualitative

- Patient views and experience of the intervention and trial procedures, assessed through qualitative interviews at 2 weeks after randomisation with five women at each study site (total 25 interviews) (See Topic Guide). Questions to be explored include:
 - Are the online trial procedures acceptable to participants? E.g. the process of online registration and consent, the receipt of incentives, completing online questionnaires, contact and follow up by email and text
 - What are women's views of the intervention?
 - How might trial procedures be improved, to optimise retention in a full-scale trial?

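### The pregnancy outcome, as the protocol words it, does not separate a pregnancy already present at enrolment from one conceived after randomisation

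*Protocol*

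**What the plan says.** Protocol section 8 lists the secondary outcome as "Pregnancy by 6 months measured at 3 months and at 6 months by response to study outcome questionnaire". Section 10.4 describes how it is collected, at follow-up and not at baseline: "participants will be asked if they have had a pregnancy and, if they have, the outcome of the pregnancy". The answers offered are "ongoing, gave birth, miscarried, terminated, or prefer not to say".

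In the same paragraph of section 10.4, the time frame "or since enrolling in the study (at follow-up" belongs to the contraceptive methods used, not to pregnancy. The sexually transmitted infection item there is asked at baseline as well as at follow-up; the pregnancy item is not.

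The five settings in section 4 include "A maternity service (Ashford & St Peter's Hospitals NHS Foundation Trust" and an abortion service, each with a target of 80 women. Under section 10.1 a future need for contraception is enough for eligibility, so women who are currently pregnant can enter. Section 4 says the trial will "follow them up by online questionnaire at 3 and 6 months (or 2 months after delivery for post-partum women", and section 10.2 repeats this timing.

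Section 10.5 restricts the analysis of long-acting reversible contraception (LARC) use to women who are not pregnant or trying to conceive. It sets no corresponding rule for the pregnancy outcome.

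**The concern.** A website that helps women choose contraception can only prevent pregnancies that have not yet begun. A woman enrolled while pregnant in a maternity or abortion service could truthfully report that pregnancy at follow-up, and the birth and termination answers fit it exactly. A conception after enrolment could hardly reach term within 6 months, so the birth answer will mostly record pregnancies present at enrolment.

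Such pregnancies are fixed before randomisation and should be spread evenly over the arms. They do not bias the comparison in one direction, but they add the same number of unavoidable events to each arm and pull the relative effect toward no difference.

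Three things are at stake:

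- Pregnancy is the outcome closest to the stated purpose of reducing unintended pregnancy.
- The budget impact analysis in the Health Economics part of section 10.5 totals the cost of pregnancy outcomes, and would include births and abortions the website could not have averted.
- The pilot is to lead to a protocol for a definitive trial (section 7), so the definition may carry forward.

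**Working it through.** **Inputs from the protocol.** Five settings of 80 plus 530 more from the sexual health site: 5 × 80 + 530 = 930, which agrees with section 9. Allocation is 1:1 and assumed follow-up is 70%, so 930 × 0.70 = 651 women followed. Maternity plus abortion: 2 × 80 = 160, or 160/930 = 17.2%; followed, 160 × 0.70 = 112. The protocol gives no expected pregnancy rate and no power for this outcome, so there is no stated figure to reproduce.

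**Assumptions, not in the protocol.**
- New-pregnancy risk over 6 months is 5% in control and 3% with the website.
- A share f of the 112 followed women was pregnant at enrolment. Each of them reports that pregnancy and has no second one in the window.
- These women divide equally between the arms.

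**Without pregnancies present at enrolment.** Odds ratio = (0.03/0.97) / (0.05/0.95) = 0.59.

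**With them counted.** Let I = 112 × f. The event proportion in an arm is I/651 + (1 − I/651) × p, with p = 0.05 or 0.03. New pregnancies over both arms are (651 − I) × 0.04.

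| f | I | Control | Website | Difference | Crude odds ratio | New pregnancies | I to new |
|---|---|---|---|---|---|---|---|
| 25% | 28 | 9.1% | 7.2% | 1.91 points | 0.77 | 24.9 | 1.1 to 1 |
| 50% | 56 | 13.2% | 11.3% | 1.83 points | 0.84 | 23.8 | 2.4 to 1 |
| 100% | 112 | 21.3% | 19.7% | 1.66 points | 0.90 | 21.6 | 5.2 to 1 |

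Example for f = 50%: 56/651 = 0.086. Control is 0.086 + 0.914 × 0.05 = 0.132 and website is 0.086 + 0.914 × 0.03 = 0.113. The odds ratio is (0.1134/0.8866) / (0.1317/0.8683) = 0.84.

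**Break-even.** Pregnancies present at enrolment outnumber new ones unless the new-pregnancy risk, averaged over the arms, exceeds I/(651 − I). That is 28/623 = 4.5%, 56/595 = 9.4% or 112/539 = 20.8% for f = 25%, 50% or 100%.

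**Wider range.** With control risk from 1% to 8%, halved by the website, and f from 25% to 100%, a true odds ratio of 0.48 to 0.50 is observed as 0.65 to 0.97. Pregnancies present at enrolment are then 43% to 97% of all events, so at the mild end they are a minority.

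**Power at 5% versus 3%** (two-sided 5% level). It is about 25% with 325 per arm and no pregnancies present at enrolment. With all 112 counted it is about 8%. Using only the 539 followed women from the other three settings, it is about 22%.

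**The case against.** The strongest reply has four parts.

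**The question itself is not shown.** Section 10.4 paraphrases it, and the outcome questionnaires sit in an appendix that is not available. The item may be narrower than the paraphrase. This stands as a limit on certainty. Adding a since-enrolment time frame would not be enough, though, because a pregnancy present at enrolment can still be ongoing, or can end, afterwards.

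**The analysis plan could settle it.** Section 10.11 promises a data analysis plan before database lock, and the recruitment setting is known. This stands in part. If neither baseline status nor conception timing is collected, the plan can only drop whole settings as a proxy.

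**The share pregnant at enrolment is unknown.** Some maternity women may already have delivered. This stands, and it is why the size must be shown as a range. A reader might infer a general ratio of five or more to one; under the 5% versus 3% assumption, that needs all of these women to be pregnant at enrolment and to report it.

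**The effect is not hidden.** A reader might infer that any effect would disappear. The protocol does not support that. The absolute difference falls only from 2.0 to between 1.91 and 1.66 points, and the other three settings are largely unaffected. Section 10.5 plans adjusted effects without naming the covariates. If setting were one and every woman in the two settings were an event, those strata would carry no information and the odds ratio would return to 0.59. Power is low even with clean measurement, and section 9 claims power only for LARC use.

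A reader might also extend the point to the outcome "Change in method between baseline and 6 months, indicating whether any change is to a method of greater, lesser or similar effectiveness". That does not follow. Moving from no method to an effective one after a birth or abortion is real change of the kind the trial targets. It can occur in both arms and leaves the randomised contrast valid.

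**Conclusion.** The point holds as a defect in outcome definition and data collection. Followed as written, pregnancies present at enrolment count as events, in a trial that draws 17% of its planned sample from maternity and abortion services.

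The consequence is dilution, not one-sided bias. Under assumed rates of 5% versus 3%, a true odds ratio of 0.59 would appear as about 0.77 to 0.90, depending on whether 25% or all of those women were pregnant at enrolment. The estimate rests on those assumed rates, on full reporting of such pregnancies, on 70% follow-up in every setting, and on a crude comparison. The same events would enter the pregnancy-related costs.

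Neither primary outcome is affected. The matter is worth correcting because the remedy is small and the definition may pass to the definitive trial.

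**What to change.** - Record at baseline whether the woman is currently pregnant.
- Define the outcome in section 8 as a pregnancy conceived after randomisation.
- Add one follow-up item asking whether the reported pregnancy began after joining the study.
- Apply the same definition to the pregnancy-related costs in the Health Economics part of section 10.5.

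If the questionnaire is already live, analyse the pregnancy outcome in the three settings that do not recruit through an existing pregnancy, and report the maternity and abortion settings separately.

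The cost of the full remedy is one or two extra online questions, in a trial that has deliberately shortened its questionnaires (section 10.3). The analysis-only route needs no new data, but leaves about 651 − 112 = 539 followed women for this secondary comparison.

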10.5. Pilot trial: Statistical analysis plan

This is a pilot RCT with original primary aim of assessing the success of recruitment and retention, engagement with the intervention, and the acceptability of trial procedures to participants and clinic staff. Power calculations were performed based on data from the Sexunzipped online trial, and were described earlier.

Following the amended recruitment plan our analysis now focuses on the effect size for key outcomes including contraception choice, and satisfaction with contraceptive method.

Statistical analysis

Primary analysis will be by modified intention-to-treat – basing analysis on those who complete at least one follow-up outcome questionnaire. For each outcome listed earlier we will present the percentage of participants if the outcome is binary (e.g. use of LARC) or ordinal (e.g. effectiveness of method, satisfaction with method) and the mean if the outcome is a score (e.g. quality of life) together with a 95% confidence interval. These percentages and means will be reported separately by intervention and standard care arm, and in the case of follow-up rate and recruitment rate by setting.

To formally assess differences between arms we will use logistic regression (for binary outcomes), ordinal logistic regression (for ordinal outcomes) or linear regression (for scores) reporting adjusted intervention effect measures with 95% confidence intervals.

The primary outcome of LARC use at 6 months will be analysed among women in need of contraception (not pregnant or currently trying to become pregnant) and the primary outcome of satisfaction with method will be analysed among women who are using a method at 6 months. The primary outcome of LARC use at 6 months will be analysed stratified by LARC use at baseline, leading to three intervention effects: the effect in baseline LARC users, the effect in baseline non-users, and the overall effect adjusted for baseline LARC use. In the event that over 90% of baseline LARC users in the control arm are using a LARC method at 6 months (or no longer need contraception) then the primary effect measure for this outcome will be the intervention effect in non-LARC users. If conversely fewer than 90% of baseline LARC users in the control arm are using a LARC method at 6 months then the primary effect measure will be the overall adjusted intervention effect. A further subgroup analysis will be conducted for both primary outcomes to assess, based on testing an interaction term, whether the effect of the intervention varies by setting.

Primary comparisons between arms will be based on multiple imputation where outcomes at 6 months are imputed based on outcomes at 3 months for those participants who completed the 3 month outcome questionnaire but failed to complete the questionnaire at 6 months.

Health Economics

The primary analysis will be a budget impact analysis of the website and contraception reporting the total costs to each payer (NHS (primary care versus secondary care), local government, private and out of pocket). This will reported as total cost of contraception and pregnancy outcomes for a range of different population sizes. The analysis will conform to the ISPOR good practice guidelines for budget impact analysis.²¹

Costs will include the cost of contraception (NHS and out of pocket costs), including the cost of LARC implants, sexual health service use, sexual health related primary and acute care use and the cost of pregnancy related outcomes. Resource use collected as part of the trial will be costed based on published sources including Personal Social Services Research Unit (PSSRU) reference costs and British National Formulary. The cost of the website will include ongoing maintenance costs and how these might be incurred by organisations that wish to use the website in the future. This cost will be reported for a range of difference population sizes. Any costs that each setting might incur implementing the website will also be collected and reported. In addition to the budget impact analysis of total cost for each payer, we will report descriptive statistics for each cost type. We will calculate the average total health care cost of contraception per participant for the website compared to current practice at baseline and 6 months. 95% confidence intervals for each analysis will be reported based on suitable regression models and bootstrapping.

Recent work by Public Health England has also investigated the Return on Investment of contraception. This work includes 10 year costs of unintended pregnancies. Data from this tool will be used to calculate the wider 10 year costs of the contraception choices website compared to current practice for each payer.

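### The 90% rule that selects the primary LARC effect counts different women in its two branches, so read literally both branches can apply to the same data

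*Protocol*

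**What the plan says.** Protocol section 10.5, under Statistical analysis, plans three intervention effects for LARC use at 6 months: in baseline LARC users, in baseline non-users, and overall with adjustment for baseline LARC use. A threshold then decides which is primary.

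- **First branch.** The condition opens "In the event that over 90% of baseline LARC users in the control arm are using a LARC method at 6 months (or no longer" and finishes the bracket so that women who "or no longer need contraception" also count. The consequence: "then the primary effect measure for this outcome will be the intervention effect in non-LARC users".
- **Second branch.** The condition is "If conversely fewer than 90% of baseline LARC users in the control arm are using a LARC method at 6 months", with no bracket. The consequence: "then the primary effect measure will be the overall adjusted intervention effect".

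The same paragraph restricts the outcome itself, which "will be analysed among women in need of contraception (not pregnant or currently trying to become pregnant"). No other part of the protocol says how the two branches fit together or which prevails.

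**The concern.** A rule of this kind should return exactly one primary analysis for every possible dataset. This one states its threshold with two different numerators, so the conditions are not complements. In one region of outcomes both are satisfied and they name different primary effects. At one boundary point neither is satisfied.

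LARC use at 6 months is a primary outcome and the basis of the 930-woman sample size in section 9. The two candidate effects refer to different populations (baseline non-users, or all women with adjustment) and need not agree in size or precision. If the wording is not settled in advance, the choice between them remains open in the overlap region, and closing that choice is the purpose of the rule.

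**Working it through.** The 90% is a decision threshold, not a derived figure, so the plan has no calculation to reproduce. The check is whether the two conditions exclude each other.

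**Notation.** Among control-arm baseline LARC users, let N be their number, u the number using LARC at 6 months, and k the number no longer needing contraception.

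- First branch: (u + k)/N > 0.90
- Second branch: u/N < 0.90

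**Overlap.** Both hold whenever u < 0.9N < u + k. Take N = 78, u = 68, k = 4:

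- First branch: 72/78 = 92.3%, over 90%, so the effect in non-users is primary.
- Second branch: 68/78 = 87.2%, under 90%, so the overall adjusted effect is primary.

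**Gap.** If k = 0 and u = 0.9N exactly, neither strict inequality holds. This needs 0.9N to be a whole number, so it can arise at N = 80 or 100 but not at N = 78 (0.9 × 78 = 70.2).

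**Does it matter which single statistic was meant?** Three consistent definitions are available. The third is the one on the primary analysis set.

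| N, u, k | (u + k)/N | u/N | u/(N − k) |
|---|---|---|---|
| 78, 68, 4 | 72/78 = 92.3% | 68/78 = 87.2% | 68/74 = 91.9% |
| 100, 85, 8 | 93/100 = 93% | 85/100 = 85% | 85/92 = 92.4% |
| 100, 76, 15 | 91/100 = 91% | 76/100 = 76% | 76/85 = 89.4% |

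Each column gives one answer, but the columns can fall on opposite sides of 90%. In the first two rows u/N disagrees with the other two. In the third row (u + k)/N and u/(N − k) disagree.

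**How often could both branches hold?** The protocol gives neither 6-month LARC continuation nor the share leaving need, so these are assumptions. For N, section 9 gives 930 × 0.70 / 2 = 325.5 followed women per arm. Section 6 gives 24% LARC use under age 30 in specialist community services, and 0.24 × 325.5 ≈ 78. Applying that 24% to all sites is also an assumption. Multinomial enumeration of P(u < 0.9N < u + k) for N = 78 gives:

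| True LARC use at 6 months | Out of need | Chance that both branches hold |
|---|---|---|
| 75% | 5% | under 1% |
| 80% | 5% | 8% |
| 84% to 92% | 1% | 3% to 12% |
| 84% to 92% | 3% | 13% to 35% |
| 84%, 86%, 88%, 90%, 92% | 5% | 31%, 47%, 55%, 48%, 28% |

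With 7% out of need, the maximum over 84% to 92% use rises to 69%. With N = 114 (35% of 325.5, itself an assumption) and 5% out of need, the range over 84% to 92% use is 20% to 63%.

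**The case against.** The best defence is the word conversely, which opens the second branch. It presents that branch as the opposite of the first, so the bracket was probably meant to carry over. On that reading there is no overlap. This stands as a likely intention and points to loose drafting rather than two deliberate definitions. It does not settle the rule, because the text does not repeat the bracket and other consistent readings can select differently.

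A second defence is the restriction to women in need of contraception. If only the second branch is read on that population, as u/(N − k), with the first as written, the overlap nearly vanishes: at most about 0.2% for N = 78 with 5% out of need and 80% to 92% LARC use, and at most about 8% for N = 114. But that reading mixes two denominators. If the restriction governed both branches, the bracket would have nothing to count.

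A reader might go further and infer any of the following, none of which the documents support:

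- **That overlap is likely.** The higher probabilities come from assumed LARC use close to 90%. The protocol gives no rate that places the trial there.
- **That the choice will be made with results in hand.** Section 10.11 says a data analysis plan will be agreed before the database is locked, and section 10.4 says the primary-outcome statisticians are blinded to allocation. The wording can be settled in time, and all three effects are planned in any case.
- **That neither branch fits the primary analysis set.** The second branch's numerator, women on LARC, does fit. Only its denominator differs.

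**Conclusion.** The concern holds as a defect in a stated decision rule. Read literally, the two branches of section 10.5 are not complementary: they overlap whenever u < 0.9N < u + k, and they leave exactly 90% unassigned when no woman has left need. This follows from the wording alone and needs no assumed rate.

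The practical size is uncertain. For N = 78 the chance of overlap is under 1% at 75% LARC use with 5% out of need, 3% to 12% at 84% to 92% use with 1% out of need, and 28% to 55% over the same use with 5% out of need. All of these rest on assumed continuation, assumed departure from need and an assumed N. The finding is therefore that the rule can give contradictory instructions, not that it probably will. It deserves correction because it governs a primary outcome and the repair is trivial.

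**What to change.** Before database lock, and before any results by arm are seen, define one statistic, use it in both branches, and assign the boundary to one of them.

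- **Minimal edit.** Repeat the bracket "or no longer need contraception" in the second branch, and set the branches as over 90% against 90% or fewer. This keeps the first branch's statistic, (u + k)/N, and removes both the overlap and the gap.
- **Acceptable alternative.** Use the percentage on LARC among control-arm baseline LARC users still in need of contraception at 6 months, u/(N − k), in both branches, and drop the bracket. This matches the primary analysis set. Its downside is that it can change which branch applies: with 76 on LARC and 15 out of need among 100, the minimal edit gives 91% and the alternative 89.4%.

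Either is sound, and the sponsor must choose one in advance. The cost is one sentence in section 10.5, carried into the data analysis plan, with no new data.
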